#### 7.5 Multiple Testing

[figure not shown]
As this study is focused on learning and hypothesis generation and does not control for multiple comparisons.

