## 4 Study Objectives and Endpoints

### 4.1 Study Objectives

#### Protocol 1

**Specific Aim 1:** Utilizing a prospective randomized clinical trial study design, we will determine whether heat therapy improves **blood pressure** (both in clinic and ambulatory) better than dynamic aerobic exercise, the gold-standard non-pharmacological treatment of essential HTN. Specifically, we hypothesize that 30 sessions of passive heat therapy using hot water immersion over 8-10 weeks will improve blood pressure in HTN individuals to a greater extent than 30 sessions of exercise training over the same time period.

**Specific Aim 2:** We will determine whether heat therapy will improve biomarkers of arterial health and compare responses to exercise training. We hypothesize that 30 sessions of heat therapy will improve arterial stiffness in HTN to a greater extent than exercise. Furthermore, we hypothesize key clinical biomarkers of systemic inflammation and oxidative stress will be improved following heat therapy.

**Specific Aim 3:** In an exploratory aim, we will determine whether the acute decreases in blood pressure following an initial heat therapy session or exercise peak test predict the sustained reduction in resting blood pressures following heat therapy treatment or exercise training in HTN. These findings would provide significant predictive information beyond baseline resting blood pressures. We hypothesize that the reduction in blood pressure following acute stressors will be predictive of treatment effects on resting blood pressure.

#### Protocol 2

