**Table 1. Outcomes by Protocol and Aim**

Protocol 1			
Outcomes	Aim 1	Aim 2	Aim 3
Primary	Clinic systolic and diastolic pressures; Ambulatory systolic and diastolic pressures	Pulse Wave Velocity (measure of arterial stiffness)	Acute and chronic pressure reductions
Secondary	Heart rate; Cardiac output; Stroke volume; Total peripheral resistance; Secondary BP outcomes: waking, sleeping, dipper vs. non-dipper	Blood-borne biomarkers	
Protocol 2			
	Cognitive	Brain biomarkers of ADRD risk	
Primary Outcomes	Memory domain composite score*	Arterial transit time: mean perfusion in gray matter, mean perfusion in white matter	

\*average of age-corrected list-sorting and age-corrected picture sequence z-scores

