**Table 3. Non-derived variables used in study assessments**

Variable	Aim/Primary or Secondary	Description
Protocol 1		
syst_bp_mean	Aim 1/Primary	Continuous; average of 3 systolic BP measurements collected in clinic at pre-, interim-, and post-intervention timepoints
diast_bp_mean	Aim 1/Primary	Clinic diastolic BP; Continuous; average of 3 diastolic BP measurements at 2 screening

		visits collected in clinic at pre-, interim-, and post-intervention timepoints
mean_rest_hr	Aim 1/Secondary	Continuous; average of 3 resting heart rate measurements collected in clinic at pre-, interim-, and post-intervention timepoints
Mean_qc	Aim 1/Secondary	Continuous; average of 3 cardiac output measurements collected in clinic at pre-, interim-, and post-intervention timepoints
Mean_qc	Aim 1/Secondary	Continuous; average of 3 cardiac output measurements collected in clinic at pre-, interim-, and post-intervention timepoints
Protocol 2		
mean_pcalib_gm	Brain biomarkers of ADRD/primary	Continuous; Mean perfusion calibration in gray matter, measure of arterial transit time
mean_pcalib_wm	Brain biomarkers of ADRD/primary	Continuous; Mean perfusion calibration in white matter measured by MRI, measure of arterial transit time

Note: means calculated in REDCap are not considered derived variables for the purposes of this table.

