## 6 Sample Size

**Projected effect sizes.** To estimate effect size for the primary outcome variables of systolic and diastolic blood pressures, we bracketed over several scenarios with varying pre- to post-intervention differences (i.e., with the fall in pressure following heat therapy being 4.0, 4.5, or 5.0 mmHg greater than following exercise training), and using a SD of 4.5 mmHg from our pilot work and published studies using similar interventions and approaches, which resulted in minimum hypothesized effect sizes of 0.89, 1.00, and 1.11 for Aim 1. For MSNA, we used a pre-intervention mean value of 39 $\pm$ 7 bursts/100beats based on our pilot data with 4 HTN subjects, and determined that a post-intervention mean value of 29 $\pm$ 7 b/100bts would represent a clinically significant change (of 10 b/100bts). Thus, for MSNA,  $d = 1.43$ .

Similarly, from our pilot work and our published studies using similar interventions and approaches, calculated effect sizes for  $\beta$ -stiffness  $d = 1.43$ , DAC  $d = 1.70$ , sympathetic baroreflex  $d = 1.33$ , FMD  $d = 2.55$ , carotid wall thickness  $d = 3.33$ , for Aim 2. Effect sizes for blood pressures were the lowest of our outcome variables; thus, powering for blood pressure will allow adequate power for numerous measurements giving us a global picture cardiovascular and autonomic health.

**Statistical power.** Our prospective power estimates based on a simpler model (two-sample RCT design, modeled as a two-sample t-test), to detect a minimum hypothesized effect size of 0.89 (which is smallest effect size of interest across outcome variables; power 90%;  $\alpha=0.05$ ), indicate the need to enroll 50 subjects (50:50 ratio of study groups; sample size assumes 20% dropout for the per-protocol analysis).

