## 9 Efficacy Analyses

For primary analyses for Protocol 1 Aims 1, primary outcomes will be compared between groups (heat therapy vs exercise training) over time (within subject repeated measurements) using two-way repeated measures mixed model including an interaction between intervention group and timepoint with pre-defined contrasts. For Specific Aim 1, to test the hypothesis that heat therapy improves blood pressure (both in clinic and 24H ambulatory) better than dynamic aerobic exercise, the null hypothesis will be that the interaction between group and timepoint is equal to 0. For Aim 2, to determine whether heat therapy will improve biomarkers of arterial health (arterial stiffness & biomarkers of systemic

inflammation and oxidative stress) and compare responses to exercise training, the null hypothesis will be that the interaction between intervention group and timepoint is equal to 0. For Aims 1 and 2 exploratory analyses, ANCOVA will be performed for primary and secondary outcomes, with pretest values entered as a covariate and treatment condition specified as a fixed factor. Demographic and physiological variables (age, sex, BMI) and pre-intervention blood pressure will be added one at a time to the ANCOVAs to test for an interaction on treatment effects. For Aim 3, we will use ANCOVA models to determine the predictive potential of acute post-exercise hypotension response for chronic changes in blood pressure, with pretest values entered as a covariate and systolic and diastolic blood pressure specified as a fixed factor. Analyses will be performed on the Intention to Treat population. Additionally, change from pre- to post-intervention in ambulatory and in clinic systolic and diastolic pressure will be correlated with change from pre- to post first intervention session supine systolic and diastolic blood pressure by Pearson correlation.

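### Aim 1 tests one superiority hypothesis on four primary blood pressure outcomes with no success rule and no multiplicity control, although it is sized as a single test at alpha 0.05

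*SAP*

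**What the plan says.** SAP Table 1 (section 4.2) gives the Aim 1 primary outcomes as "Clinic systolic and diastolic pressures; Ambulatory systolic and diastolic pressures". Tables 3 and 4 label the four corresponding variables as Aim 1 primary.

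SAP section 4.1 states the hypothesis that heat therapy "will improve blood pressure in HTN individuals to a greater extent than 30 sessions of exercise training over the same time period". Section 9 restates it as "heat therapy improves blood pressure (both in clinic and 24H ambulatory) better than dynamic aerobic exercise" and says that "the null hypothesis will be that the interaction between group and timepoint is equal to 0". The model is described as "including an interaction between intervention group and timepoint with pre-defined contrasts", but the contrasts are not listed. Each outcome has three timepoints; for example, clinic systolic pressure is the "average of 3 systolic BP measurements collected in clinic at pre-, interim-, and post-intervention timepoints".

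SAP section 6 and the sample size paragraph in Protocol section C size the trial with one two-sample t-test at alpha 0.05. The effect size is 0.89, "which is smallest effect size of interest across outcome variables; power 90" per cent, with 50 enrolled and 20% dropout. The Protocol says that 40 completers are needed.

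On multiplicity, SAP section 7.5 has one sentence: "As this study is focused on learning and hypothesis generation and does not control for multiple comparisons". Neither document orders the four outcomes, sets a test-level alpha for them, or says which pattern of results would support Aim 1.

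**The concern.** The reason given in section 7.5 does not fit the rest of the plan. A study run only to generate hypotheses needs neither a directional superiority hypothesis against the gold-standard non-drug treatment nor a sample size built on alpha and power. The SAP also marks what it regards as exploratory, namely Aim 3 and the ANCOVAs in section 9.1. The Aim 1 mixed-model comparisons are not so marked.

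With four primaries and no rule, the headline claim can be settled after the results are known. One significant outcome could be reported as heat therapy lowering blood pressure more than exercise. A stricter reader could require both settings and both pressures. These two rules have very different error rates and power, and the single alpha and power in section 6 cannot describe both.

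**Working it through.** **Inputs.** Four primary outcomes (SAP Table 1). Smallest difference 4.0 mmHg and SD 4.5 mmHg, so d = 4.0/4.5 = 0.89 (SAP section 6). Alpha 0.05, power 90%, 50 enrolled 1:1, 20% dropout (SAP section 6, Protocol section C). Sidedness is not stated; I take two-sided, in keeping with a null of zero interaction. The documents give no correlations between outcomes, so these are assumed and varied.

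**Step 1: the plan's own figure.** Per arm, n = 2(z₁₋α/₂ + z₁₋β)²/d².
- 90% power: 2(1.960 + 1.282)²/0.89² = 26.5, so 27 (28 by the t distribution). That is 54 to 56 completers, and dividing by 0.8 gives 68 to 70 enrolled.
- 80% power: 2(1.960 + 0.842)²/0.89² = 19.8, so 20. That is 40 completers, and 40/0.8 = 50 enrolled.

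So 50 enrolled and 40 completers match 80% power by the normal approximation, not 90%. The two-sided t-test has 78.3% power with 20 per arm and 86.9% with 25. One-sided at 0.05 it has 86.8% and 92.7%, so 90% is reached only with a one-sided test and no dropout.

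**Step 2: four tests, each two-sided at 0.05.** If independent, the chance of at least one false positive is 1 − 0.95⁴ = 18.5%. Blood pressure outcomes are correlated, so I simulated two-sample t-tests on four correlated normal outcomes, with d = 0.89 on every outcome for power. The first column gives the assumed correlations: systolic with diastolic by the same method / same pressure across methods / different pressure and method. Error rates barely differ between 20 and 25 per arm. False heat superiority has a nominal rate of 2.5%.

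| Correlations | Any false difference | False heat superiority | Any-of-four power, 20 / 25 per arm | All-four power, 20 / 25 per arm |
|---|---|---|---|---|
| 0.3 / 0.3 / 0.15 | 18% | 9% | 99% / >99% | 45% / 62% |
| 0.6 / 0.4 / 0.3 | 16% | 8% | 97% / 99% | 51% / 67% |
| 0.7 / 0.6 / 0.45 | 14.5% | 7% | 95% / 98% | 56% / 70% |
| 0.8 / 0.7 / 0.6 | 13% | 6.5% | 93% / 97% | 60% / 73% |
| 0.9 throughout | 9.5% | 4.7% | 87% / 93% | 68% / 79% |

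**Step 3: what each rule does.** Under an any-of-four rule the error rate fails and power is roughly as stated. Under an all-four rule each test is at 0.05, so the joint error stays at or below 0.05 and only power fails.

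**Not counted.** Reading the interim and post contrasts separately would add tests.

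**The case against.** The lack of adjustment is disclosed and a reason is given, so nothing is hidden. That stands, but disclosure does not reconcile the reason with a sized superiority test. A figure in section 7.5 is not shown in the text available to me; the sentence beside it still says that there is no control.

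The phrase about clinic and ambulatory pressure may only name the measurement settings and not require success in both. That also stands, and it is why no rule can be inferred.

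Twenty per arm is the pessimistic case. The 20% dropout is tied to the per-protocol analysis, whereas the primary analysis is intention-to-treat by a mixed model that tolerates missing values. Results for 25 per arm are therefore shown as well. Also, 0.89 is the smallest of three effect sizes. At d = 1.11, all-four power over the table's correlations is about 77% to 88% with 20 per arm and 90% to 94% with 25. But section 6 attaches its 90% to 0.89.

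A reader might infer that both stated figures fail whichever rule applies. The documents do not support that: each rule breaks one figure, apart from the separate single-outcome power problem. Nor is the error always three times 5%; at correlation 0.9 it is about twice. Nor is the whole power gap a multiplicity effect: the fall from 90% to 78% or 87% is already there with one outcome.

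**Conclusion.** The concern holds. Aim 1 is framed and sized as confirmatory, has four primary outcomes with no rule for combining them, and is excused from multiplicity control for a reason that conflicts with that framing.

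The size depends on the missing rule. Under any-of-four, the familywise error is about 9% to 18%, and about 4.7% to 9% for false heat superiority. Under all-four, the shortfall is in power alone. These figures rest on assumed correlations, two-sided tests, and the same standardised effect on all four outcomes. The t-test is the plan's own simplification; the mixed model may behave somewhat differently.

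The 90% power statement is a separate fault. It needs correcting whichever success rule is adopted, and a multiplicity fix alone will not repair it.

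**What to change.** First establish whether the Aim 1 arm comparisons have been seen. SAP section 8.2 reports a deviation found during analysis, section 9.1 describes some correlations as already performed, and section 13 records changes in April and May 2024 after residual plots had been assessed. Some data had therefore been examined; the documents do not show whether this included the Aim 1 comparisons.

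- **If unseen:** name one Aim 1 primary contrast. One candidate is the arm difference in pre-to-post change in 24-h ambulatory systolic pressure; the ambulatory paragraph in Protocol section C itself argues that ambulatory readings predict outcome better than office readings. Test the other three blood pressure outcomes in a fixed written order at 0.05, stopping at the first failure. Date the change and state that the comparisons were unseen. Limit the section 7.5 sentence to the remaining analyses, without relabelling pulse wave velocity or the Protocol 2 primaries.
- **If seen:** a new order would not be prespecified. Report all four outcomes with unadjusted intervals and drop the confirmatory superiority wording.
- **In both cases:** correct the power statement. For one two-sided test at d = 0.89 it is 78% with 20 per arm and 87% with 25; 90% would need 68 to 70 enrolled.

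The cost is wording and no new data. The downside of the ordered sequence is that later blood pressure outcomes can be claimed only if those ahead of them succeed. The choice and order of outcomes are for the investigators to justify.

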### 8 Summary of Study Data

Continuous variables will be summarized as: mean (standard deviation), median (IQR), and frequency % as appropriate for parametric, nonparametric, and categorical variables, respectively. Summary tables will be structured with a column for study group (Heat Therapy, Exercise Training) and overall and will be annotated with the total population size relevant to that table/treatment, including any missing observations.

#### 8.1 Subject Disposition

A consort flow diagram will be created using study coordinator tracked numbers of pre-screenings and screenings not fully captured in REDCap. In-person screening numbers determined in REDCap by those with redcap\_event\_name values of "screening\_visit\_1\_arm\_1." Exclusion reasons determined for age, systolic BP, diastolic BP, pregnant/nursing/trying to conceive, BMI, HbA1c, glucose, total LDL, cardiovascular disease, medications, and IPAQ category of physical activity values for REDCap instrument screening\_day\_1\_data\_sheet variables age, syst\_bp\_mean, diast\_bp\_mean, preg\_nurse\_conc, bmi, hba1c, gluc, tot\_ldl, cvd, drugs, and ipaq\_cat respectively. Participants enrolled was determined based on ID list from clinical coordinators. Participants randomized determined by having a value for the intervention variable int in the REDCap randomization instrument.

## 8.2 Protocol Deviations

Protocol deviations uncovered during analysis included one Heat Therapy participant that should have been excluded for LDL values  $\geq 160$  who completed the study. Following published recommendations on handling of ineligible participants that are inadvertently randomized, this participant is included in the intention to treat analysis dataset.

## 8.3 Demographic and Baseline Variables

The following variables for sex, age, race, ethnicity, body mass index (BMI), glycated hemoglobin (HbA1c), total cholesterol, high-density lipoprotein (HDL), low-density lipoprotein (LDL), LDL/HDL ratio, non-HDL, triglycerides, fasting glucose, total cholesterol, mean systolic BP, mean diastolic BP, and heart rate will be described at baseline: sex, age, race, ethnic\_group, bmi, hba1c, tot\_chol, hdl, , tot\_ldl, ldl\_hdl, non\_hdl, triglyc, gluc, tc\_hdl, syst\_bp\_mean, diast\_bp\_mean, and hr\_mean. Summary statistics will be reported as described in section 9.

## 8.4 Treatment Compliance

Compliance will be defined as participation in Heat Therapy or Exercise Training intervention visits.

## 9 Efficacy Analyses

For primary analyses for Protocol 1 Aims 1, primary outcomes will be compared between groups (heat therapy vs exercise training) over time (within subject repeated measurements) using two-way repeated measures mixed model including an interaction between intervention group and timepoint with pre-defined contrasts. For Specific Aim 1, to test the hypothesis that heat therapy improves blood pressure (both in clinic and 24H ambulatory) better than dynamic aerobic exercise, the null hypothesis will be that the interaction between group and timepoint is equal to 0. For Aim 2, to determine whether heat therapy will improve biomarkers of arterial health (arterial stiffness & biomarkers of systemic

inflammation and oxidative stress) and compare responses to exercise training, the null hypothesis will be that the interaction between intervention group and timepoint is equal to 0. For Aims 1 and 2 exploratory analyses, ANCOVA will be performed for primary and secondary outcomes, with pretest values entered as a covariate and treatment condition specified as a fixed factor. Demographic and physiological variables (age, sex, BMI) and pre-intervention blood pressure will be added one at a time to the ANCOVAs to test for an interaction on treatment effects. For Aim 3, we will use ANCOVA models to determine the predictive potential of acute post-exercise hypotension response for chronic changes in blood pressure, with pretest values entered as a covariate and systolic and diastolic blood pressure specified as a fixed factor. Analyses will be performed on the Intention to Treat population. Additionally, change from pre- to post-intervention in ambulatory and in clinic systolic and diastolic pressure will be correlated with change from pre- to post first intervention session supine systolic and diastolic blood pressure by Pearson correlation.

For Protocol 2, where composite score cognitive function and brain biomarkers of ADRD risk outcomes were not collected at the interim timepoint, separate linear regressions will be performed for each outcome and predictor combination, where the post-intervention timepoint of the measure is the outcome, the pre-intervention measure of the outcome will be included as a covariate, and predictors will be intervention group in Aim 1 and 24H ambulatory systolic and diastolic blood pressure and arterial stiffness measures mean perfusion calibration in gray matter or white matter in Aim 2. Diagnostic plots and Cook's D of linear regressions will be assessed for influential outliers. If found and not improved through transformation, Robust regression using Huber weighting will be utilized instead.

Continuous outcomes will be transformed for normalcy prior to analysis. Methods used to check model assumptions will include checking for extreme outliers by visual inspection and Shapiro test and checking for homogeneity of variance by visual inspection and Levene's test. Full model results will be saved in an appendix or csv file, for possible use in planning future studies, meta-analysis and to enable replication of analysis.

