PRE-TESTS: Before and after the INTERVENTION, we will conduct high-resolution phenotyping of subjects which will include: lab-based hemodynamic tests of vascular function; blood-based biomarkers related to cardiovascular health; 24-h urine collection; 24-h food/beverage log; 24-h ambulatory blood pressure recording; VO₂peak fitness test. These are detailed below *Specific Experimental Approaches*.

ASSIGN: Subjects will be randomized to either the heat therapy group or exercise training group, then undergo 30 sessions of the specific intervention at a rate of 3-4 per week over an 8 to 10-week period. Randomization will be stratified by age and sex to ensure equal numbers within each stratum. Further stratification, for example by BMI or initial blood pressure, would be difficult given the small sample size. (More details of the randomization process are under *Randomization*). After the first 15 sessions, subjects will be re-tested for hemodynamic and biomarker adaptations to the intervention (INTERIM-TEST). After 30 sessions, subjects will undergo final POST-TESTS.

INTERVENTION: Subjects in the **heat therapy** group will report to the lab to undergo heat therapy sessions 3-4 times per week, with 45 minutes of hot water immersion per session. The goal of heat therapy is to maintain core temperature above 38.5°C for at least 30 min. This target has previously been shown to be the threshold temperature and time exposure to optimize adaptations to passive heat exposure¹¹. Subjects in our lab, including sedentary, hypertensive, obese, and spinal cord-injured subjects, have tolerated this heating protocol very well. Subjects will be checked for euhydration prior to entering the tub and will be monitored closely throughout heating for heart rate and blood pressure during all sessions. In addition, core temperature (T_{core} ; FDA approved ingestible core temp sensing pill; Accutemp Temperature Monitoring System by HQ Inc.) will be monitored during the first 5 and final sessions whereas aural temperature may be monitored in all sessions. Subjects will be removed from the hot bath if T_{core} exceeds 39.5°C. Water immersion is the preferred method of heating since it is capable of increasing core temperature and heart rate at a rate similar to moderate-intensity exercise¹². Subjects in the **exercise training** group will report to the lab for a supervised exercise training session 3-4 times per week. We will use heart rate

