### 7.3 Covariates and Subgroups

#### Protocol 1

Protocol 1 covariates included in analyses in section 9.1 include age, sex, body mass index,

pre-intervention 24 hour ambulatory systolic and diastolic blood pressure, and average of three systolic and diastolic blood pressure readings prior to the first Heat Therapy or Exercise Training session.

#### Protocol 2

Protocol 2 covariates/potential confounders that will be characterized for their relationship with each other and Protocol 1 and 2 outcomes as described in section 9.1 include are listed in **Table 5**.

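### The primary Aim 1 and Aim 2 model uses the pre-intervention value only by subtraction; a baseline-adjusted primary model would be modestly more precise on average

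*SAP*

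**What the plan says.** SAP section 9 compares the arms over time for Aim 1 with a "two-way repeated measures mixed model including an interaction between intervention group and timepoint with pre-defined contrasts". For Aim 1, "the null hypothesis will be that the interaction between group and timepoint is equal to 0"; for Aim 2, "the null hypothesis will be that the interaction between intervention group and timepoint is equal to 0". The pre-intervention reading is one of the repeated responses: SAP Table 3 defines clinic systolic pressure as the "average of 3 systolic BP measurements collected in clinic at pre-, interim-, and post-intervention timepoints".

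Baseline adjustment appears only in the exploratory tier: "For Aims 1 and 2 exploratory analyses, ANCOVA will be performed for primary and secondary outcomes, with pretest values entered as a covariate". SAP 7.3 ties the Protocol 1 covariates to the exploratory section as well: "Protocol 1 covariates included in analyses in section 9.1 include age, sex, body mass index" (the list goes on to pre-intervention pressures). No section states a baseline covariate, or a constraint of equal pre means, for the primary model.

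Two further passages bear on this:

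- Initial blood pressure is not a randomisation stratum. Protocol section C (ASSIGN) explains: "Further stratification, for example by BMI or initial blood pressure, would be difficult given the small sample size".
- In Protocol 2 the main regressions in SAP 9 do take the pre-intervention value as a covariate. SAP 13 says this was possible because those measures have no interim visit.

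**The concern.** Randomisation makes the true pre-intervention means equal in the two arms. A model that lets them differ spends information on a difference known to be zero in expectation. Its pre-to-post interaction contrast then reduces to the difference in mean change, which weights the baseline by exactly 1 instead of by its regression slope. A chance difference in initial pressure is therefore over-corrected, and it is not controlled by stratification either.

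At stake are some precision and the clarity of the Aim 1 conclusion. The same data will be analysed by an interaction model called primary and an ANCOVA called exploratory, and the two can fall on opposite sides of 0.05. The trial has little power to spare, so even a modest gain from data already collected is worth taking.

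**Working it through.** **Inputs.** From SAP 6: a difference in fall of 4.0 mmHg, SD 4.5 mmHg, effect size 0.89, alpha 0.05, power 90%, two-sample t-test, 50 enrolled with 20% dropout. From the Protocol's power paragraph: 40 completers, so 20 per arm. Three assumptions are needed: the test is two-sided; 4.5 mmHg is the SD of change (the documents do not say, but the effect size is set on a difference in falls); and the between-person SD is 6 to 10 mmHg. The pre-post correlation rho is not given.

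**The plan's own figure.** For effect size 0.89, two-sided 0.05 and 90% power, the normal approximation needs 27 per arm (54 completers, 68 enrolled). The t-test needs 28 per arm (56 and 70). The stated 50 is not reproduced at 90%; it matches 80% by the normal approximation (20 per arm, 40, 50). With 20 per arm the planned comparison has 80% power (normal) or 78% (t). That mismatch is a separate point; here 78% is the starting value.

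**The planned contrast is a change-score comparison.** A random-intercept mixed model with group, time and their interaction, fitted to one balanced simulated data set, gave a post-by-group coefficient of -5.976. The difference in mean change in the same data was -5.976.

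**Variance.** With equal pre and post variances sigma² and n per arm:

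- change score: 4·sigma²·(1 - rho)/n
- baseline-adjusted: 2·sigma²·(1 - rho²)/n
- ratio, adjusted to change: (1 + rho)/2

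This is a large-sample ratio. Estimating the slope with N = 40 multiplies it by about 1 + 1/(N - 4) = 37/36.

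**Plausible rho.** SD of change² = 2·SD²·(1 - rho), so rho = 1 - 4.5²/(2·SD²):

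- SD 6: 1 - 20.25/72 = 0.72
- SD 8: 1 - 20.25/128 = 0.84
- SD 10: 1 - 20.25/200 = 0.90

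**Power for 4.0 mmHg, 20 per arm.** The change score has 78%. The adjusted figures use noncentral t with 37 df and the 37/36 factor.

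| rho | (1 + rho)/2 | with 37/36 | adjusted power |
|---|---|---|---|
| 0.50 | 0.75 | 0.77 | 88% |
| 0.72 | 0.86 | 0.88 | 83% |
| 0.84 | 0.92 | 0.95 | 80% |
| 0.90 | 0.95 | 0.98 | 79% |
| 0.95 | 0.975 | 1.00 | 78% |

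**How often the two analyses differ.** 20,000 simulated trials per setting, with a true 4 mmHg effect:

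| rho | ANCOVA alone significant | change score alone significant | verdicts differ | ANCOVA SE at least as large |
|---|---|---|---|---|
| 0.72 | 7.2% | 2.3% | 9.5% | 16% |
| 0.84 | 4.5% | 2.6% | 7.1% | 34% |
| 0.90 | 3.2% | 2.5% | 5.7% | 47% |

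**Chance imbalance.** A one-SD difference between arm pre means is SD·sqrt(2/n). With 25 per arm it is 1.7 mmHg (SD 6) to 2.8 mmHg (SD 10). It moves the change-score estimate by (1 - rho) times that: 0.28 × 1.7 = 0.5 and 0.10 × 2.8 = 0.3 mmHg. With 20 per arm the range is again 0.3 to 0.5. The standard error of the estimate is 4.5·sqrt(2/20) = 1.4 mmHg.

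**The case against.** The planned analysis is legitimate. It uses the baseline, by subtraction. It is unbiased over randomisation and its type I error is valid. Baseline-adjusted ANCOVA is already specified for every primary and secondary outcome, with model formulae for interim and post pressure in SAP 9.1, so readers will see both results. SAP 7.5 describes the study as hypothesis-generating. All of this stands: the question is only which of two valid analyses is called primary.

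The contrasts are also not spelled out. With three visits the overall interaction has 2 degrees of freedom and includes the interim visit, so pre-to-post is the natural reading but not a stated one.

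Timing is the most serious practical objection. SAP 13 and the output list record revisions into May 2024, SAP 8.2 mentions a deviation found during analysis, and SAP 13 says residual plots had been inspected before the Protocol 2 model was changed. The documents do not say whether Protocol 1 outcomes had been examined by arm. If they had, promoting ANCOVA would be a post-hoc change, and the fix must allow for that.

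A reader might infer that the primary estimate always has the larger standard error. It does not: the variance ratio holds on average and in large samples, and within a single trial the ANCOVA standard error was often at least as large. A reader might also infer that switching could only help the trial meet Aim 1, but the simulations show reversals both ways, with ANCOVA favoured more often.

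**Conclusion.** The point holds as a low-severity suggestion, something to consider. The primary model forgoes baseline adjustment that the collected data allow and that Protocol 2 already uses. An interim visit is no obstacle to it.

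Under the two SD assumptions the gain is about 1 to 5 percentage points of power (78% to between 79% and 83%). It would be larger if rho were lower, about 88% at rho 0.5, and it disappears near rho 0.95. The choice of primary model changed the significance verdict in roughly 6% to 10% of simulated trials.

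Two stronger readings are not supported. First, a gain of about 10 points, or the equivalent of a third more patients (1/0.75 = 1.33), needs rho 0.5. With a 4.5 mmHg SD of change, that means a between-person SD of only 4.5 mmHg, and the documents give no correlation to justify it. Second, the primary result is not biased in the usual sense: the shift is conditional on an observed imbalance and is 0.3 to 0.5 mmHg for a one-SD imbalance, against a standard error of about 1.4 mmHg.

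If 4.5 mmHg is instead the SD of a single reading, the absolute powers change but the ratio (1 + rho)/2 does not.

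**What to change.** In SAP 9, keep the mixed model on pre, interim and post values for Aims 1 and 2, but give both arms one common pre mean, with group effects only at interim and post. An alternative is to model interim and post with the pre value and its interaction with timepoint as covariates. Name the post-visit group difference as the reported contrast, and keep the present unconstrained interaction model as a sensitivity analysis.

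If Protocol 1 outcomes have already been examined by arm, record the date and reason for the change in SAP 13 and report both models side by side.

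The cost is one paragraph of SAP text and a few lines of R, with no new data.
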